- 107 Willing to maintain current general diet and physical activity regimen, except for the physical activity in the 72 hours before each blood sample collection for the clinical laboratory analysis, which should not be strenuous
- 108 Female subjects must be of non-reproductive potential (cohorts1-6)

Postmenopausal as defined as:

- Age of ≥ 55 years with no menses for at least 12 months; OR
- Age < 55 with no menses within the past 12 months AND with a follicle-stimulating hormone level > 40 IU/L or according to the definition of "postmenopausal range" for the laboratory involved; OR
- History of hysterectomy; OR
- History of bilateral oophorectomy
- 109 Male subjects must agree to practice an acceptable method of effective birth control while on study through 5 months after receiving study drug. Acceptable methods of effective birth control include sexual abstinence; vasectomy; or a condom with spermicide (males) in combination with barrier methods (diaphragm, cervical cap or cervical sponge), hormonal birth control or IUD (females)
- 110 Male subjects must be willing to abstain from sperm donation while on study through 5 months after receiving study drug
- 111 For cohort 7, currently on liraglutide 3.0 mg SC QD with history of taking liraglutide 3.0 mg SC QD continuously for ≥ 6 months and liraglutide being generally well tolerated per the investigator's discretion (and subjects plan to continue liraglutide 3.0 mg SC QD)

6.2 Exclusion Criteria: Part 1

Subjects are excluded from the study if any of the following criteria apply:

Other Medical Conditions

- History or clinical evidence of diabetes mellitus, including a fasting glucose
 ≥ 125 mg/dl (6.9 mmol/L) and/or HbA1c > 6.5% at screening
- 202 Triglycerides ≥ 5.65 mmol/L (ie, 500 mg/dL) at screening

203	Hepatic liver enzymes ALT, AST, alkaline phosphatase (ALP), or total bilirubin (TBIL) levels > 1.5 (cohorts 1-6) or > 2 (cohort 7) times the upper limit of normal (ULN) at screening
204	History or clinical evidence of bleeding diathesis or any coagulation disorder, including prothrombin time (PT), activated partial thromboplastin time (APTT), International normalized ratio (INR) or platelet count outside of the laboratory's normal reference range at screening
205	Untreated or uncontrolled hypothyroidism/hyperthyroidism defined as thyroid-stimulating hormone > 6 mIU/L or <0.4 mIU/L

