12.7 Appendix 7. Hepatotoxicity Stopping Rules: Suggested Actions and Follow-up Assessments

Subjects with abnormal hepatic laboratory values (ie, alkaline phosphatase [ALP], aspartate aminotransferase [AST], alanine aminotransferase [ALT], total bilirubin [TBL]) and/or international normalized ratio (INR) and/or signs/symptoms of hepatitis (as described below) may meet the criteria for withholding or permanent discontinuation of Amgen investigational product or other protocol-required therapies, as specified in the *Guidance for Industry Drug-Induced Liver Injury: Premarketing Clinical Evaluation, July 2009*.

Criteria for Withholding and/or Permanent Discontinuation of Amgen Investigational Product and Other Protocol-required Therapies Due to Potential Hepatotoxicity

The following stopping and/or withholding rules apply to subjects for whom another cause of their changes in liver biomarkers (TBL, INR and transaminases) has not been identified.

Important alternative causes for elevated AST/ALT and/or TBL values include, but are not limited to:

- Hepatobiliary tract disease
- Viral hepatitis (eg, hepatitis A/B/C/D/E, Epstein-Barr Virus, cytomegalovirus, herpes simplex virus, varicella, toxoplasmosis, and parvovirus)
- Right sided heart failure, hypotension or any cause of hypoxia to the liver causing ischemia
- Exposure to hepatotoxic agents/drugs or hepatotoxins, including herbal and dietary supplements, plants and mushrooms
- Heritable disorders causing impaired glucuronidation (eg, Gilbert's syndrome, Crigler-Najjar syndrome) and drugs that inhibit bilirubin glucuronidation (eg, indinavir, atazanavir)
- Alpha-one antitrypsin deficiency
- Alcoholic hepatitis
- Autoimmune hepatitis
- Wilson's disease and hemochromatosis
- Nonalcoholic fatty liver disease including steatohepatitis
- Non-hepatic causes (eg, rhabdomyolysis, hemolysis)

If investigational product(s) is/are withheld, the subject is to be followed for possible drug induced liver injury (DILI) according to recommendations in the last section of this appendix.

Rechallenge may be considered if an alternative cause for impaired liver tests (ALT, AST, ALP) and/or elevated TBL, is discovered and the laboratory abnormalities resolve to normal or baseline (see next section in this appendix).

Table 12-2. Conditions for Withholding and/or Permanent Discontinuation ofAmgen Investigational Product and Other Protocol-required Therapies Due toPotential Hepatotoxicity

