Analyte	Temporary Withholding	Permanent Discontinuation
TBL	> 3x ULN at any time	> 2x ULN
		OR
INR		> 1.5 (for subjects not on anticoagulation therapy)
	OR	AND
AST/ALT	 > 8x ULN at any time > 5x ULN but < 8x ULN for ≥ 2 weeks > 5x ULN but < 8x ULN and unable to adhere to enhanced monitoring schedule > 3x ULN with clinical signs or symptoms that are consistent with hepatitis (such as right upper quadrant pain/tenderness, fever, nausea, vomiting, and jaundice) 	In the presence of no important alternative causes for elevated AST/ALT and/or TBL values > 3x ULN (when baseline was < ULN)
	OR	
ALP	> 8x ULN at any time	

ALP = alkaline phosphatase; ALT = alanine aminotransferase; AST = aspartate aminotransferase; INR = international normalized ratio; TBL = total bilirubin; ULN = upper limit of normal

Criteria for Rechallenge of Amgen Investigational Product and Other Protocol-required Therapies After Potential Hepatotoxicity

The decision to rechallenge the subject should be discussed and agreed upon

unanimously by the subject, Principal Investigator, and Amgen.

If signs or symptoms recur with rechallenge, then the study drug should be permanently discontinued. Subjects who clearly meet the criteria for permanent discontinuation (as described in Table 12-2) are never to be rechallenged.

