12.7.1 Drug-induced Liver Injury Reporting and Additional Assessments

Reporting

To facilitate appropriate monitoring for signals of DILI, cases of concurrent AST or ALT and TBL and/or INR elevation, according to the criteria specified in the above, require the following:

- The event is to be reported to Amgen as a serious adverse event within 24 hours of discovery or notification of the event (ie, before additional etiologic investigations have been concluded)
- The appropriate Case Report Form (CRF) (eg, Event CRF) that captures information necessary to facilitate the evaluation of treatment-emergent liver abnormalities is to be completed and sent to Amgen

Other events of hepatotoxicity and potential DILI are to be reported as serious adverse events if they meet the criteria for a serious adverse event defined in Section 12.4.

Additional Clinical Assessments and Observation

All subjects in whom investigational product(s) or protocol-required therapies is/are withheld (either permanently or conditionally) due to potential DILI as specified in Table 12-2 or who experience AST or ALT elevations > 3 x upper limit of normal (ULN) or 2-fold increases above baseline values for subjects with elevated values before drug are to undergo a period of "close observation" until abnormalities return to normal or to the subject's baseline levels.

Assessments that are to be performed during this period include:

- Repeat AST, ALT, ALP, bilirubin (BIL) (total and direct), and INR within 24 hours
- In cases of TBL > 2x ULN or INR > 1.5, retesting of liver tests, BIL (total and direct), and INR is to be performed every 24 hours until laboratory abnormalities improve

Testing frequency of the above laboratory tests may decrease if the abnormalities stabilize or the investigational product(s) or protocol-required therapies has/have been discontinued AND the subject is asymptomatic.

Initiate investigation of alternative causes for elevated AST or ALT and/or elevated TBL. The following are to be considered depending on the clinical situation:

- Complete blood count with differential to assess for eosinophilia
- Serum total immunoglobulin (Ig)G, anti-nuclear antibody anti-smooth muscle antibody, and liver kidney microsomal antibody-1 to assess for autoimmune hepatitis
- Serum acetaminophen (paracetamol) levels
- A more detailed history of:
 - Prior and/or concurrent diseases or illness
 - o Exposure to environmental and/or industrial chemical agents

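### Table 12-2 requires no hold or stop for an asymptomatic subject with baseline AST/ALT at or above ULN who reaches AST/ALT > 3x to 5x ULN with TBL > 2x to 3x ULN or INR > 1.5

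*Protocol*

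**What the plan says.** **Permanent discontinuation (protocol Section 12.7, Table 12-2).** Either TBL > 2x ULN or an INR "> 1.5 (for subjects not on anticoagulation therapy") is needed, joined by AND to the AST/ALT entry: "In the presence of no important alternative causes for elevated AST/ALT and/or TBL values > 3x ULN (when baseline was < ULN"). No entry covers a baseline at or above ULN.

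**Temporary withholding (same table).** Any one of these suffices, with no baseline condition:
- TBL > 3x ULN
- AST/ALT > 8x ULN
- AST/ALT > 5x to < 8x ULN, if it lasts 2 weeks or more or the subject cannot keep up the extra monitoring
- AST/ALT "> 3x ULN with clinical signs or symptoms that are consistent with hepatitis"
- ALP > 8x ULN

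INR has no entry in this column.

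**Entry.** Criterion 203 (Section 6.2) excludes liver tests at "levels > 1.5 (cohorts 1-6) or > 2 (cohort 7) times the upper limit of normal (ULN) at screening". The cohort 7 re-check on day 1 (criterion 112, Section 6.3) lists history, examination, vital signs and ECG, but no laboratory results.

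**Follow-up (Section 12.7.1).** Close observation applies at AST/ALT > 3x ULN and also to "2-fold increases above baseline values for subjects with elevated values before drug". TBL > 2x ULN or INR > 1.5 brings retesting every 24 hours, and a search for other causes is started. The 24-hour SAE report covers "cases of concurrent AST or ALT and TBL and/or INR elevation, according to the criteria specified in the above".

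**The concern.** Concurrent transaminase and bilirubin or INR elevation without another explanation is the pattern for which the protocol orders permanent discontinuation with no rechallenge. The baseline clause removes from that rule every subject whose AST/ALT was at or above ULN before dosing. The entry criteria allow such subjects, and Section 12.7.1 recognises them. If no withholding entry catches them, identical on-study results lead to a mandatory stop in one subject and to individual discretion in another. In cohort 7 that discretion is spread over about 30 sites.

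At stake are any AMG 598 doses still to come and continued daily liraglutide, since Table 12-2 governs both. Prompt reporting is also unclear, because the SAE trigger refers back to criteria that carry the baseline clause.

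**Working it through.** The plan states no figure for this point. The check is whether the two columns of Table 12-2, read together, leave a region uncovered.

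**Rules as written.** Let a = AST/ALT, t = TBL, p = ALP and b = baseline AST/ALT (all as multiples of ULN), and r = INR.

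- Hold = t > 3, or a > 8, or [5 < a < 8 and (2 weeks or more, or monitoring not kept up)], or [a > 3 with hepatitis signs or symptoms], or p > 8.
- Stop = (t > 2 or r > 1.5) and a > 3 and b < 1, with no alternative cause.

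**Subject.** No symptoms, monitoring kept up, p = 1, not on an anticoagulant, no alternative cause found.

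**Worked case.** a = 4.0, t = 2.5, r = 1.0. Hold: 2.5 is not > 3, 4.0 is neither > 8 nor between 5 and 8, there are no symptoms, and ALP is normal, so no hold. Stop: 2.5 > 2 and 4.0 > 3 both hold, so only b decides. At b = 0.8 the subject stops permanently. At b = 1.0, 1.5 or 2.0 nothing is required. With a = 4.0, t = 1.0 and r = 1.6 the result is the same.

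**Grid.** The narrow box takes a = 3.1, 4, 5 with (t, r) = (2.1, 1.0), (2.5, 1.0), (3.0, 1.0), (1.0, 1.6), (2.5, 1.6), which gives 3 × 5 = 15 points. The wider grid takes a = 3.1, 4, 5, 6, 7.9, 8.0, 8.1 and adds (3.1, 1.0), which gives 7 × 6 = 42 points.

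| Baseline AST/ALT | Narrow box: neither hold nor stop | Wider grid, rise under 2 weeks: neither |
|---|---|---|
| 0.8x ULN | 0 of 15 | 0 of 42 |
| 1.0x ULN | 15 of 15 | 30 of 42 |
| 1.5x ULN | 15 of 15 | 30 of 42 |
| 2.0x ULN | 15 of 15 | 30 of 42 |

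The narrow-box result is unchanged if the rise lasts 4 weeks. The 30 are six AST/ALT values (3.1 to 8.0) × five pairs with TBL at or below 3x. The other 12 are held, either because AST/ALT is 8.1x or because TBL is 3.1x. The gap therefore extends to AST/ALT > 5x to < 8x ULN when the rise has lasted under 2 weeks and monitoring is kept up. These counts describe what the rule covers, not how often subjects would fall there.

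**AMG 598 doses at stake in cohort 7.** Doses fall on days 1, 29 and 57. Post-dose chemistry falls on days 29 and 57 (both pre-dose), 85, 145 and 207 (Table 2-3).

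| First detected | Doses still to be given |
|---|---|
| Day 29, result back before injection | 2 |
| Day 29, result back after injection | 1 |
| Day 57, result back before injection | 1 |
| Day 57, result back after injection | 0 |
| Day 85, 145 or 207 | 0 |

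Table 2-3 sends chemistry to the central laboratory, while Table 12-1 heads it as local, so a same-visit result cannot be assumed. Only the 30 of 60 subjects assigned AMG 598 have AMG 598 exposure at stake.

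**The case against.** The strongest defence is that these subjects are watched closely and can be stopped. Section 12.7.1 requires close observation, retesting and a cause work-up. Section 8 lets the investigator or sponsor withdraw treatment. Section 7.4.2.1 gives cohort 7 an unblinded medical monitor and a Safety Surveillance Team (SST) that may recommend altering or ending dosing. Steatohepatitis and Gilbert's syndrome are listed alternative causes, so some raised-baseline subjects fall outside the rules altogether. Several conditions must coincide. A baseline clause can also be defended, because a subject starting at 2.0x ULN passes 3x after a 3.1/2.0 = 1.55-fold rise.

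Most of this stands, and it limits the point to a missing required pause. It does not close the gap, because none of these provisions sets a liver threshold at which this subject must be held. The argument about a small relative rise bears on an irreversible stop more than on a temporary hold.

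A reader might go further and infer that a hold without an alternative cause is already a stop. The text says "Rechallenge may be considered if an alternative cause for impaired liver tests (ALT, AST, ALP) and/or elevated TBL, is discovered". It does not say that this is the only route, and it expressly bars rechallenge for subjects who clearly meet the permanent criteria and if signs or symptoms recur on rechallenge. A reader might also infer that the 24-hour SAE report excludes these cases. The wording leaves that open, with this fallback: "Other events of hepatotoxicity and potential DILI are to be reported as serious adverse events if they meet the criteria" of the general definition.

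**Conclusion.** The gap is real on the text of Table 12-2, and closing it is a cheap safety improvement. It applies to a subject with baseline AST/ALT at or above ULN who has no symptoms, no identified alternative cause and ALP at or below 8x ULN. The uncovered results are AST/ALT > 3x to 5x ULN (or > 5x to < 8x for under 2 weeks with monitoring kept up), plus either TBL > 2x to 3x ULN, or INR > 1.5 off anticoagulation with TBL at or below 3x ULN. Symptomatic subjects are covered by the withholding column.

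For a cohort 7 subject assigned AMG 598, the doses at stake are none, one (typically detection on day 29) or at most two. Continued daily liraglutide is left to judgment. The documents do not give the number of subjects affected.

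Three stronger readings are not supported:
- **Remaining exposure as the expected loss.** A reader might count all remaining AMG 598 and liraglutide as lost protection. That is a ceiling: late detection leaves no AMG 598 dose, half of cohort 7 is on placebo, and mandatory retesting makes months of inaction a worst case.
- **Criterion 203 as a limit on baseline.** It applies at screening, whereas the SAP takes baseline as the last assessment before first dose.
- **Cohorts 1-6 as nearly finished with dosing.** The review before cohort 7 needed only 6 of 8 cohort 6 subjects through day 36, and replacements are allowed, so the number of doses left there cannot be bounded from the documents.

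**What to change.** 1. Add to the temporary-withholding column of Table 12-2: *AST/ALT > 3x ULN with TBL > 2x ULN or INR > 1.5 (not on anticoagulation), regardless of baseline*. Keep it under the appendix's existing restriction to subjects without another identified cause. Every point on the 42-point grid has AST/ALT of at least 3.1x with TBL of at least 2.1x or INR 1.6, so none is left uncovered at any baseline. The entry also supplies the missing INR hold.
2. State in Section 12.7.1 that the 24-hour SAE report applies to this combination whatever the baseline.
3. Leave any permanent-discontinuation limb for raised baselines to the sponsor's hepatic-safety experts. The documents give no basis for choosing its threshold.

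The cost is one table entry and one sentence by amendment, with no new sample, visit or procedure. The downside is that a few subjects with raised baseline AST/ALT or bilirubin may be held after a small change. For example, ALT 2.0x to 3.1x (1.55-fold) with TBL 1.9x to 2.1x ULN (2.1/1.9 = 1.1-fold) would pause both AMG 598 and liraglutide, and resuming may be difficult if no alternative cause is found.

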12.7.1 Drug-induced Liver Injury Reporting and Additional Assessments

Reporting

To facilitate appropriate monitoring for signals of DILI, cases of concurrent AST or ALT and TBL and/or INR elevation, according to the criteria specified in the above, require the following:

- The event is to be reported to Amgen as a serious adverse event within 24 hours of discovery or notification of the event (ie, before additional etiologic investigations have been concluded)
- The appropriate Case Report Form (CRF) (eg, Event CRF) that captures information necessary to facilitate the evaluation of treatment-emergent liver abnormalities is to be completed and sent to Amgen

Other events of hepatotoxicity and potential DILI are to be reported as serious adverse events if they meet the criteria for a serious adverse event defined in Section 12.4.

Additional Clinical Assessments and Observation

All subjects in whom investigational product(s) or protocol-required therapies is/are withheld (either permanently or conditionally) due to potential DILI as specified in Table 12-2 or who experience AST or ALT elevations > 3 x upper limit of normal (ULN) or 2-fold increases above baseline values for subjects with elevated values before drug are to undergo a period of "close observation" until abnormalities return to normal or to the subject's baseline levels.

Assessments that are to be performed during this period include:

- Repeat AST, ALT, ALP, bilirubin (BIL) (total and direct), and INR within 24 hours
- In cases of TBL > 2x ULN or INR > 1.5, retesting of liver tests, BIL (total and direct), and INR is to be performed every 24 hours until laboratory abnormalities improve

Testing frequency of the above laboratory tests may decrease if the abnormalities stabilize or the investigational product(s) or protocol-required therapies has/have been discontinued AND the subject is asymptomatic.

Initiate investigation of alternative causes for elevated AST or ALT and/or elevated TBL. The following are to be considered depending on the clinical situation:

- Complete blood count with differential to assess for eosinophilia
- Serum total immunoglobulin (Ig)G, anti-nuclear antibody anti-smooth muscle antibody, and liver kidney microsomal antibody-1 to assess for autoimmune hepatitis
- Serum acetaminophen (paracetamol) levels
- A more detailed history of:
 - Prior and/or concurrent diseases or illness
 - o Exposure to environmental and/or industrial chemical agents
 - Symptoms (if applicable) including right upper quadrant pain, hypersensitivity-type reactions, fatigue, nausea, vomiting and fever
 - Prior and/or concurrent use of alcohol, recreational drugs and special diets
 - Concomitant use of medications (including non-prescription medicines and herbal and dietary supplements), plants, and mushrooms

- Viral serologies
- Creatine phosphokinase, haptoglobin, lactate dehydrogenase and peripheral blood smear
- Appropriate liver imaging if clinically indicated
- Appropriate blood sampling for pharmacokinetic analysis if this has not already been collected
- Hepatology consult (liver biopsy may be considered in consultation with a hepatologist)

Follow the subject and the laboratory tests (ALT, AST, TBL, INR) until all laboratory abnormalities return to baseline or normal or considered stable by the investigator. The "close observation period" is to continue for a minimum of 4 weeks after discontinuation of all investigational product(s) and protocol-required therapies.

The potential DILI event and additional information such as medical history, concomitant medications and laboratory results must be captured in the corresponding CRFs.

Subjects with an increase in score on either the PHQ-9 and/or CSSR-S assessments

may meet the criteria for permanent discontinuation of Amgen investigational product or

other protocol-required therapies.

Criteria for Withholding and/or Permanent Discontinuation of Amgen Investigational Product and Other Protocol-required Therapies Due to Potential Mental Health Changes

The following stopping rules apply to subjects for whom an increase in their PHQ-9

and/or CSSR-S sores have been identified.

Table 12-3. Conditions for Permanent Discontinuation of Amgen InvestigationalProduct and Other Protocol-required Therapies Due to Changes in Mental HealthScores

Mental Health Assessment	Permanent Discontinuation
PHQ-9	≥ 10
	OR
CSSR-S	Answers yes to any items #1-5

PHQ-9 = Patient Health Questionnaire 9; CSSR-S = Columbia Suicide Severity Rating Scale

Reporting

To facilitate appropriate monitoring for signals of mental health changes according to the criteria specified in the above, require the following:

- The event is to be reported to Amgen as a serious adverse event within 24 hours of discovery or notification of the event (ie, before additional etiologic investigations have been concluded)
- The appropriate Case Report Form (CRF) (eg, Event CRF) that captures information necessary to facilitate the evaluation of treatment-emergent liver abnormalities is to be completed and sent to Amgen

Additional Clinical Assessments and Observation

All subjects in whom investigational product(s) or protocol-required therapies is/are withheld permanently due to potential mental health changes as specified in Table 12-3 are to undergo a period of "close observation" until the subject's care can be transferred to an appropriate mental health professional.

